9.5.1.3. Long-term Efficacy Analysis

Long-term efficacy of the primary vaccination series with mRNA-1273 will be evaluated after the primary analysis by including data collected in the Open-Label Observational Phase (Part B). Long-term efficacy data will be summarized descriptively by treatment cohort described in [Table 10](#) without cohort comparison. The long-term efficacy endpoints are listed in

[Table 11](#) with the same case definitions specified in [Table 1](#). In the primary approach, cases will be counted starting 14 days after the second dose of IP for participants in treatment cohorts of mRNA-1273 and placebo or starting 14 days after the second dose of mRNA-1273 for participants in the Placebo-mRNA-1273 Cohort. Sensitivity analyses with cases starting from the second dose, 14 days after the first dose, or first dose of IP for participants in the cohorts of mRNA-1273 and placebo, or mRNA-1273 for participants in the Placebo-mRNA-1273 Cohort may be provided. Incidences of cases assessed by numbers, rates, and 2-sided 95% CI based on the exact method adjusting for person-time will be summarized by treatment cohort. The Kaplan-Meier analysis will be used to estimate cumulative incidences of time to first cases by treatment cohort. Long-term efficacy analysis will be performed using the PP Set and mITT Set.

Efficacy analyses of unblinded/open-label phase data collected in Part B will be provided, as measured by the incidence rate of COVID-19 after the BD of mRNA-1273. The details of analysis of long-term efficacy and open-label phase data (Part B and Part C) will be provided in the SAP.

Table 10: Treatment Cohorts for the Long-term Efficacy Analyses

Treatment Cohort	Description
mRNA-1273	Participants randomized to mRNA-1273 in the Blinded Phase.
Placebo	Participants randomized to Placebo in the Blinded Phase and did not crossover to mRNA-1273 in the Open-Label Observational Phase.
Placebo-mRNA-1273	Participants randomized to Placebo in the Blinded Phase and crossed over to mRNA-1273 in the Open-Label Observational Phase.

Table 11: Long-term Efficacy Endpoints

Long-term Efficacy Endpoint

Cases of COVID-19 starting 14 days after the second injection of:
 
 • IP for participants in the mRNA-1273 Cohort and the Placebo Cohort, 
or
 
 • mRNA-1273 for participants in the Placebo-mRNA-1273 Cohort.

Cases of severe COVID-19 starting 14 days after the second injection of:
 
 • IP for participants in the mRNA-1273 Cohort and the Placebo Cohort, 
or
 
 • mRNA-1273 for participants in the Placebo-mRNA-1273 Cohort.

Cases of either COVID-19 or SARS-CoV-2 infection starting 14 days after the second injection of:
 
 • IP for participants in the mRNA-1273 Cohort and the Placebo Cohort, 
or
 
 • mRNA-1273 for participants in the Placebo-mRNA-1273 Cohort.

Cases with a secondary (less restrictive) definition of COVID-19 starting 14 days after the second injection of:
 
 • IP for participants in the mRNA-1273 Cohort and the Placebo Cohort, 
or
 
 • mRNA-1273 for participants in the Placebo-mRNA-1273 Cohort.

Cases of death due to a cause directly attributed to a complication of COVID-19, starting 14 days after the second injection of:
 
 • IP for participants in the mRNA-1273 Cohort and Placebo Cohort, 
or
 
 • mRNA-1273 for participants in the Placebo-mRNA-1273 Cohort.

Cases of COVID-19 starting 14 days after the first injection of:
 
 • IP for participants in the mRNA-1273 Cohort and the Placebo Cohort, 
or
 
 • mRNA-1273 for participants in the Placebo-mRNA-1273 Cohort.

Regardless of evidence of prior SARS-CoV-2 infection determined by serologic titer against SARS-CoV-2 nucleocapsid, cases of COVID-19 starting 14 days after the second injection of:
 
 • IP for participants in the mRNA-1273 Cohort and the Placebo Cohort, 
or
 
 • mRNA-1273 for participants in the Placebo-mRNA-1273 Cohort.

Cases of SARS-CoV-2 infection in the absence of symptoms defining COVID-19 starting 14 days after the second injection of:
 
 • IP for participants in the mRNA-1273 Cohort and the Placebo Cohort, 
or
 
 • mRNA-1273 for participants in the Placebo-mRNA-1273 Cohort.

Abbreviations: COVID-19 = coronavirus disease 2019; IP = investigational product; SARS-CoV-2 = severe acute respiratory syndrome coronavirus 2.

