A clinical study report (CSR) has been developed based on the final analysis of the randomized blinded phase (Part A) dated 03 August 2021. Efficacy, safety and immunogenicity of Part A have been analyzed and reported in the CSR for Part A. A CSR addendum presenting safety and efficacy results of the Part B Open-label phase was developed based on the database lock on 04 May 2021.

Therefore, analyses of blinded phase (Part A) data are considered to be completed.

This SAP Part B and Part C focuses on the OL phase and BD phase of the study and provides statistical analysis details/data derivations focusing on Part B and Part C. The SAP Part B and Part C will also provide more details for the unblinded phase (Part B) analyses that were briefly described in SAP Version 2.0, dated 08-MAR-2021. In addition, methods for analysis of the primary series based on Part B and Part A, and for mRNA-1273 using data across parts is included.

Modifications or additions to the analysis plan which are not “principal” in nature is also documented, if the methods in this SAP Part B and Part C differ from the methods described in the protocol, the SAP will prevail.

PPD Biostatistics and programming team, designee of Moderna Biostatistics and Programming department, will perform the statistical analysis; Statistical Analysis System (SAS) Version 9.4 or higher will be used, and R or RStudio may be used.

In this document, subject and participant are used interchangeably; injection of IP, injection, and dose are used interchangeably; vaccination group and treatment group are used interchangeably; Part A and the blinded phase are used interchangeably; Part B and the Open-label (OL) phase are used interchangeably; Part C and the booster dose (BD) phase are used interchangeably; treatment groups and treatment cohorts are used interchangeably; titers and levels are used interchangeably.

2. Study Objectives

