5.1.4. Analysis Strategy and Treatment Groups

Analyses Strategy: The following analyses may be performed by using Part B and Part C data. Please also refer to “Analysis Periods” subsection (Section 5.1.5) in this section. The analysis periods are summarized in Table 1 of Section 5.1.5.

- To assess effectiveness and safety during Part B (OL-phase period), analyses may be conducted using the analysis periods and treatment groups for Efficacy and Safety of Part B based on data collected in Part B.
- To assess the effectiveness and safety after booster (Part C), Part C analyses will be conducted using the analysis periods and treatment groups for Effectiveness and Safety of Part C based on data collected during the booster dose phase (Part C).
- To assess effectiveness of the primary series of mRNA-1273, analyses of effectiveness may be conducted using analysis periods and treatment groups for efficacy using data collected in Part A and Part B. Please note only those who received 2 doses of mRNA-1273 would be included in the analyses.
- To assess effectiveness of a booster, and long term effectiveness (or durability) of mRNA-1273 primary series, analysis of effectiveness may be conducted using analysis periods and treatment groups for efficacy using data collected during the blinded phase (Part A), the open-label phase (Part B), and the booster dose phase (part C).

Treatment cohorts/groups

The following treatment groups have been used in analysis of blinded phase (Part A):

- mRNA-1273
- Placebo

The following treatment groups have been and will be used in analysis of Part B:

- mRNA-1273
- Placebo-mRNA-1273
- Placebo

The above 3 treatment groups may also be used to assess long term effectiveness of mRNA-1273 (Part A and Part B).

If a participant requested to receive mRNA-1273 in Part B (OL phase), the subject will be included to mRNA-1273 cohort as the planned treatment group for efficacy analysis, regardless whether the dose was actually received or not. Participants who were randomized to placebo and planned to receive mRNA-1273 in the open-label phase will be included to the Placebo-mRNA-1273 Cohort for efficacy analysis. Participants who only received placebo in the blinded phase and received mRNA-1273 in the open-label phase will be included in the Placebo-mRNA-1273 Cohort for safety analysis and efficacy analysis for Part B.

The following treatment groups will be used in analysis of Part C:

- Booster 50 µg after mRNA-1273 Primary Series

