5.3.1.2. Analysis approach for effectiveness of vaccine

COVID-19 will be evaluated using incidence rates. Number of events and incidence rate will be provided in a dynamic approach for each treatment cohort, e.g., a participant without COVID-19 or SARS-COV-2 infection will no longer be considered as “at risk” in the non-booster treatment group from the timepoint when this participant received the booster dose, instead, this participant will be considered as “at risk” in the booster treatment group from that timepoint. Incidence rate will be calculated as the number of

participants with an event divided by the number of subjects at risk adjusted by person-time (years) in each treatment cohort.

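### The protocol's long-term Placebo cohort is selected on a later event and drops crossovers' placebo time; the SAP corrects this for Part B but not for its optional pooling of Parts A and B

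*Protocol*

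**What the plan says.** Protocol 9.5.1.3 summarises long-term efficacy by three cohorts. Table 10 puts in the Placebo cohort "Participants randomized to Placebo in the Blinded Phase and did not crossover to mRNA-1273 in the Open-Label Observational Phase". The main counting rule is this: "cases will be counted starting 14 days after the second dose of IP for participants in treatment cohorts of mRNA-1273 and placebo", and, for those who crossed over, "starting 14 days after the second dose of mRNA-1273 for participants in the Placebo-mRNA-1273 Cohort". Case numbers, person-time rates with exact intervals and Kaplan-Meier curves are to be given by cohort, "without cohort comparison". The protocol adds: "The details of analysis of long-term efficacy and open-label phase data (Part B and Part C) will be provided in the SAP".

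The SAP for Part B and Part C states in its Introduction that "if the methods in this SAP Part B and Part C differ from the methods described in the protocol, the SAP will prevail". For Part B effectiveness, its Table 1 (Section 5.1.5) starts follow-up at PDV/unblinding and assigns Placebo by not having requested mRNA-1273. Section 5.3.1.2.1 limits the Part B risk set to participants with no earlier COVID-19 or infection and a non-positive status at PDV. Section 5.3.1.2 says: "Number of events and incidence rate will be provided in a dynamic approach for each treatment cohort".

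After listing mRNA-1273, Placebo-mRNA-1273 and Placebo as the Part B groups, Section 5.1.4 continues: "The above 3 treatment groups may also be used to assess long term effectiveness of mRNA-1273 (Part A and Part B". Table 1 has no Placebo row for that combined use; its primary-series rows contain only the two vaccinated groups.

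**The concern.** Under the protocol wording, a placebo recipient's membership of the Placebo cohort is settled at or after PDV, but the case clock starts months earlier. The mRNA-1273 cohort carries no such condition: it is everyone randomized to vaccine. Only the placebo side is selected on its own future.

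If having been a case makes crossover less likely, the Placebo cohort keeps a larger share of its early cases than of its early person-time, and its rate is too high. For a COVID-19 death before PDV this is certain, because such a participant cannot cross over, and COVID-19 death is one of the endpoints in Protocol Table 11. At stake is the credibility of the long-term placebo rates and curves, which will be read beside those of the vaccine cohorts even though no comparison is planned.

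**Working it through.** No figure in the plan depends on this point, so there is none to reproduce. The check has two parts.

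**1. Where placebo-arm follow-up goes under Protocol 9.5.1.3**

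- Never-crossers, from day 14 after Part A Dose 2: Placebo cohort, before and after PDV.
- Crossovers, up to the first mRNA-1273 dose: no long-term cohort. The time up to PDV/unblinding is used in the Part A efficacy analysis (Part A SAP, Sections 6.1 and 6.4.3).
- Crossovers, from day 14 after the second mRNA-1273 dose: Placebo-mRNA-1273 cohort.

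**2. Size of the bias**

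Input from the documents: planning incidence 0.75% in 6 months on placebo (Protocol 9.3), so the hazard is −ln(1 − 0.0075)/0.5 = 0.01506, or 15.1 per 1,000 person-years.

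Assumptions not in the documents:
- a = 0.33 years from day 14 after Dose 2 to PDV, and b = 1.5 years after it.
- A constant hazard, equal in crossers and never-crossers.
- Probability of not crossing over: q0 if event-free at PDV, q1 if already a case; k = q1/q0.

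For rare events the pre-PDV rate is inflated by about k, and the overall rate by about (a·k + b)/(a + b) = (0.33k + 1.5)/1.83. For k = 2 this is 2.16/1.83 = 1.18; for k = 3 it is 2.49/1.83 = 1.36.

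One case in full, per placebo participant, with q0 = 0.10 and q1 = 0.20:
- Probability of a case before PDV: 1 − exp(−0.01506 × 0.33) = 0.00496.
- Before PDV: events 0.00496 × 0.20 = 0.00099; person-years 0.00496 × 0.20 × 0.165 + 0.99504 × 0.10 × 0.33 = 0.0330; rate 30.0 per 1,000.
- After PDV: 0.0995 event-free never-crossers; events 0.0995 × (1 − exp(−0.01506 × 1.5)) = 0.00222; person-years 0.1476.
- Overall: (0.00099 + 0.00222)/(0.0330 + 0.1476) = 17.8 per 1,000, against a true 15.1.

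The same closed form for other values:

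| Scenario | Factor before PDV | Factor overall |
|---|---|---|
| k = 1 | 1.00 | 1.00 |
| k = 1.5 | 1.50 | 1.09 |
| k = 2 | 2.00 | 1.18 |
| k = 3 (q0 up to 0.20) | 2.99 | 1.36 |
| Event precludes crossover (q1 = 1), q0 = 0.05 | 19.1 | 4.43 |
| q1 = 1, q0 = 0.10 | 9.78 | 2.63 |
| q1 = 1, q0 = 0.20 | 4.95 | 1.73 |
| q1 = 1, q0 = 0.40 | 2.49 | 1.27 |

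At five times the hazard the overall factors hardly move: 1.09, 1.19 and 1.37 for k = 1.5, 2 and 3, and 4.42 to 1.28 for q1 = 1. With k = 1 there is no bias, but 60% (q0 = 0.40) to 95% (q0 = 0.05) of the pre-PDV placebo person-time is still discarded.

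A simulation of 2,000,000 participants at five times the planning hazard, with q0 = 0.10 and q1 = 0.10, 0.20, 0.30 and 1.0, compared three rules. The Table 10 rule gave 1.00, 1.19, 1.38 and 2.66 times the true rate. Counting all placebo time and censoring at crossover gave 1.00 to 1.01. The SAP rule (from PDV, event-free participants) gave 0.99 to 1.01.

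**The case against.** The strongest reply is that the SAP governs and does something else. Its Part B analysis starts at PDV in event-free participants, so an earlier case cannot enter the Placebo rate. Its primary-series analysis has no placebo group. Its optional durability models (Section 5.6.1) handle crossover by inverse probability weighting or by a time-varying vaccine effect in calendar time. The dynamic person-time rule is worded for every cohort, with the booster only as an example. All of this stands, and it clears the Part B analysis.

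It does not close the combined use in SAP Section 5.1.4. For that use the SAP gives Placebo no start, no end and no rule for time before crossover, and the dynamic rule's only example concerns the booster. Section 6 of the same SAP records no changes from the protocol. The only written placebo counting rule is therefore the one in Protocol 9.5.1.3.

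Three stronger readings are tempting, and the documents do not support them:

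- A reader might infer that the placebo rate is biased for COVID-19 in general. Protocol 7.1 makes COVID-19 a reason to delay Part B dosing, or to discontinue dosing at the investigator's discretion, not an automatic bar. Study vaccine was also subject to availability (Section 4.1.2). Together these make a dependence plausible, but the documents do not show one, nor do they give the share who crossed over.
- A reader might infer that vaccine efficacy is overstated. The protocol plans no cohort comparison here, and no test, success criterion or efficacy estimate uses this cohort.
- A reader might infer that crossovers' placebo data are lost. They are missing only from the long-term cohorts.

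**Conclusion.** The point holds for the protocol's descriptive long-term summary and for any SAP analysis that pools Parts A and B by the three cohorts. It does not hold for the SAP's Part B analysis.

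Upward bias is certain for COVID-19 death before PDV: 1.3- to 4.4-fold overall if 40% down to 5% of event-free placebo recipients never cross over. For other endpoints it is conditional. If cases stay uncrossed 2 to 3 times as often, it is 2- to 3-fold before PDV and about 1.2- to 1.4-fold overall; if crossover is unrelated to case status, it is nil. The 2- to 3-fold figure should not be read as the error in the whole long-term rate.

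The sizes rest on assumed crossover shares, a constant common hazard, 0.33 years before PDV and 1.5 years after it. Shorter follow-up after PDV would move the overall factor towards the pre-PDV one. That is possible, because placebo recipients who seek vaccine outside the study are withdrawn (Protocol 7.3.1).

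**What to change.** In Protocol 9.5.1.3 and Table 10, and in SAP Part B and Part C Section 5.1.4 and Table 1, state that in any analysis pooling Parts A and B every placebo recipient contributes placebo person-time and cases until the first mRNA-1273 dose (or unblinding; name one). Those who cross over then move to Placebo-mRNA-1273. This applies the dynamic approach of SAP Section 5.3.1.2 and gives the pooled use the Placebo analysis period it lacks. The case clock for Placebo-mRNA-1273 can stay where the protocol puts it.

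Two inconsistencies should be settled at the same time:

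- The protocol defines Placebo by not crossing over, SAP Table 1 by not requesting mRNA-1273. Someone who requested it but never received it is Placebo under one and Placebo-mRNA-1273 under the other (SAP Appendix F).
- SAP Table 1 gives the Part B Placebo cohort a reference date of the first mRNA-1273 dose, which that cohort by definition did not request.

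The cost is wording and programming; no new data are needed. The change does not remove confounding by who chooses to cross over, and the report should say so.

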9.5.2. Safety Analyses

All safety analyses will be based on the Safety Set, except summaries of solicited ARs, which will be based on the Solicited Safety Set. All safety analyses will be provided by treatment group, and by treatment cohort as applicable, unless otherwise specified. Pregnancies and their known outcomes will be summarized ([Section 8.3.6](#)).

9.5.2.1. Adverse Events

Safety and reactogenicity will be assessed by clinical review of all relevant parameters. Safety analyses will be provided for Parts A, B, and C separately unless specified otherwise.

The number and percentage of participants with any solicited local AR, with any solicited systemic AR, and with any solicited AR during the 7-day follow-up period after each dose will be provided only for Part A. A 2-sided 95% exact CI using the Clopper-Pearson method will be also provided for the percentage of participants with any solicited AR for each treatment group. Analysis of solicited AR will be provided using the Solicited Safety Set for Part A.

The number and percentage of participants with unsolicited AEs (Part A [all participants] and Part C [only those who receive the BD]), SAEs, MAAEs, AESIs (Part C [only those who receive the BD]), and AEs leading to discontinuation from IP or withdrawal from the study will be summarized. Unsolicited AEs will be presented by MedDRA preferred term and system organ class. Analyses of AEs will be provided for Part A and Part B using the Safety Set. For Part C, analysis of AEs will be provided in the Part C Safety Set (ie, participants who received booster in Part C).

For all other safety parameters, descriptive summary statistics will be provided, and [Table 12](#) summarizes the analysis strategy for safety parameters. Further details will be described in the SAP.

Table 12: Analysis Strategy for Safety Parameters in Part A

Safety Endpoint	Number and Percentage of Participants, Number of Events	95% CI
Any Solicited AR (Part A; overall and by local, systemic)	X	X
Any Unsolicited AE	X	
Any SAE	X	
Any Unsolicited MAAE	X	
Any Unsolicited Treatment-Related AE	X	
Any Treatment-Related SAE	X	
Discontinuation due to AE	X	
Any Grade 3 and above AE	X	
Any Treatment-Related Grade 3 and above AE	X	

Abbreviations: AE = adverse event; AR = adverse reaction; CI = confidence interval; MAAE = medically attended adverse event; MedDRA = Medical Dictionary for Regulatory Activities; SAE = serious adverse event.

Notes: 95% CI using the Clopper-Pearson method, X = results will be provided. Unsolicited AEs will be summarized by System Organ Class and Preferred Term coded by MedDRA. Safety parameters will be analyzed in applicable study parts and participants as further specified in the statistical analysis plan.

9.5.2.2. Baseline Descriptive Statistics

Demographic variables and baseline characteristics will be summarized by treatment group, and by treatment cohort as applicable, by descriptive statistics (mean, standard deviation for continuous variable, and number and percentage for categorical variables).

9.5.3. Immunogenicity Analyses

The secondary immunogenicity endpoints will be analyzed using the Immunogenicity Subset by treatment group, by treatment cohort as applicable, and by baseline SARS-CoV-2 serostatus, unless otherwise specified. Details for immunogenicity analyses will be provided in the SAP.

The SAP will describe the complete set of immunogenicity analyses, including the approach to sample individuals into an Immunogenicity Subset for characterizing mRNA-1273 immunogenicity and assessing immunological correlates of risk and protection.

9.5.3.1. Part A

Data from quantitative immunogenicity assays will be summarized for each treatment group using positive response rates and geometric means with 95% CIs, for each timepoint for which an assessment is performed. Data from qualitative (ie, yielding a positive or negative result) assays will be summarized by tabulating the frequency of positive responses for each assay by group at each timepoint that an assessment is performed. Analyses will focus on the 2 key immunogenicity

timepoints and the change in marker response between them: Day 1 before the first dose of IP and Day 57 (28 days after the second dose of IP). The SAP will describe the complete set of immunogenicity analyses.

Quantitative levels or geometric mean titer (GMT) of specific bAb with corresponding 95% CI at each timepoint and geometric mean fold rise (GMFR) of specific bAb with corresponding 95% CI at each postbaseline timepoint over pre-dose baseline at Day 1 will be provided by study arm. Descriptive summary statistics including median, minimum, and maximum will also be provided.

The GMT of specific nAb with corresponding 95% CI at each timepoint and GMFR of specific nAb with corresponding 95% CI at each postbaseline timepoint over pre-dose baseline at Day 1 will be provided by study arm. Descriptive summary statistics including median, minimum, and maximum will also be provided. For summarizations of group values, Ab values reported as below the LLOQ will be replaced by $0.5 \times \text{LLOQ}$. Values that are reported as greater than the upper limit of quantification (ULOQ) without the actual values will be converted to the ULOQ.

The number and percentage of participants with a fold rise ≥ 2 , ≥ 3 , and ≥ 4 of serum SARS-CoV-2-specific nAb titers and participants with seroresponse from baseline will be provided with 2-sided 95% CI using the Clopper-Pearson method at each post-baseline timepoint.

Seroresponse at a participant level may be defined as a change from below the LLOQ to at least 4 times the LLOQ, or at least a 4-fold rise in nAb or vaccine antigen-specific bAb in participants with pre-existing nAb or bAb of at least the LLOQ at baseline/pre-vaccination. Seroresponse may also be defined for each specific assay assessing nAb or bAb. The definition of seroresponse will be finalized and documented in the SAP.

The GMT of specific nAb for each group and the geometric mean ratio (GMR) of mRNA-1273 versus placebo in Part A with corresponding 2-sided 95% CI will be estimated at each study timepoint using an analysis of covariance model with the treatment group and baseline values, if applicable, as explanatory variables, the analysis may adjust for the stratification factor (Table 13).

Table 13: Immunogenicity Endpoints and Statistical Methods

Endpoint	Statistical Analysis Methods
Specific bAb and nAb titers/values	
 • GMT of each group, GMR (mRNA-1273 vs. placebo) • GMT estimated by the ANCOVA model
Fold rise	
 • GMFR – descriptive statistics • Binomial endpoints of fold rise ≥ 2, 3, and 4, and seroconversion due to vaccination – the Clopper-Pearson method

Abbreviations: ANCOVA = analysis of covariance; bAb = binding antibody; GMFR = geometric mean fold rise, GMR = geometric mean ratio; GMT = geometric mean titer; nAb = neutralizing antibody.

